**Table 2-9 Safety Topics of Interest**

Safety Topic of Interest	Analysis
Anaphylaxis	Standard analyses;
Angioedema	Standard analyses;
Change in bone growth	Standard analyses;
Cognitive impairment (Broad SMQ)	Standard analyses;
Cognitive impairment (Narrow SMQ)	Standard analyses;
Embryo-fetal toxicity	Standard analyses;

Safety Topic of Interest	Analysis
Hepatotoxicity	

1. Standard analyses;

2. Summary of the shift from baseline to minimum and maximum post-baseline category (Section 2.8.3.1) in alkaline phosphatase (ALP), alanine aminotransferase (ALT), aspartate aminotransferase (AST) and total bilirubin (TBL)

3. Numbers and percentages of patients with each of the following events will be provided by treatment group, for overall and for each stratum (ACEi, ARB, No RASi);

a. (ALT > 3 × ULN) or (AST > 3 × ULN)

b. (ALT > 5 × ULN) or (AST > 5 × ULN)

c. (ALT > 8 × ULN) or (AST > 8 × ULN)

d. (ALT > 10 × ULN) or (AST > 10 × ULN)

e. (ALT > 20 × ULN) or (AST > 20 × ULN)

f. [(ALT > 3 × ULN) or (AST > 3 × ULN)] and (TBL > 1.5 × ULN)

g. [(ALT > 3 × ULN) or (AST > 3 × ULN)] and (TBL > 2 × ULN)

h. [(ALT > 5 × ULN) or (AST > 5 × ULN)] and (TBL > 2 × ULN)

i. [(ALT > 8 × ULN) or (AST > 8 × ULN)] and (TBL > 2 × ULN)

j. [(ALT > 10 × ULN) or (AST > 10 × ULN)] and (TBL > 2 × ULN)

k. [(ALT > 20 × ULN) or (AST > 20 × ULN)] and (TBL > 2 × ULN)

l. (ALP > 2 × ULN)

m. (ALP > 3 × ULN)

n. (ALP > 5 × ULN)

o. (TBL > 1.5 × ULN)

p. (TBL > 2 × ULN)

q. (TBL > 3 × ULN)

r. (ALP > 3 × ULN) and (TBL > 2 × ULN)

s. (ALP > 5 × ULN) and (TBL > 2 × ULN)

t. [(ALT > 3 × ULN) or (AST > 3 × ULN)] and [nausea or vomiting or fatigue or general malaise or abdominal pain or (rash and eosinophilia)]

u. [(ALT > 3 × ULN) or (AST > 3 × ULN)] and (TBL > 2 × ULN) and (ALP ≤ 2 × ULN)

v. [(ALT > 3 × ULN) or (AST > 3 × ULN)] and [(TBL > 2 × ULN) and (ALP ≤ 2 × ULN)] or reported Hy's Law case

w. (TBL > 3 × ULN) and [(AST ≤ 3 × ULN) or (ALT ≤ 3 × ULN)] and (ALP ≤ 1.5 × ULN)

x. (ALP > 3 × ULN) and AST, ALT, TBL are within normal range

Hyperkalemia	

1. Standard analyses;

Safety Topic of Interest	Analysis
	

2. Numbers and percentages of patients with treatment emergent hyperkalemia leading to study treatment interruption will be provided by treatment group, for overall and for each stratum (ACEi, ARB, No RASi);

3. Numbers and percentages of patients with treatment emergent hyperkalemia leading to study treatment permanent discontinuation will be provided by treatment group, for overall and for each stratum (ACEi, ARB, No RASi);

4. Numbers and percentages of patients with any post-baseline serum potassium <math>\geq 5.5</math> mEq/L, <math>>6.0</math> mEq/L and <math>>6.5</math> mEq/L will be provided by treatment group, for overall and for each stratum (ACEi, ARB, No RASi);

Hypersensitivity (Broad SMQ)	Standard analyses;
Hypersensitivity (Narrow SMQ)	Standard analyses;
Hypotension	

1. Standard analyses;

2. Blood pressures and change from baseline in blood pressures will be summarized by treatment group and visit, for overall and for each stratum (ACEi, ARB, No RASi), using number of observations, mean, standard deviation, median, minimum, Q1, Q3, and maximum;

3. Numbers and percentages of patients with the following events will be provided by treatment group, for overall and for each stratum (ACEi, ARB, No RASi);

a. Post-baseline SBP <math>< 100</math> mmHg;

b. At least 30 mmHg drop in SBP (post-baseline assessments comparing to baseline);

c. Simultaneous post-baseline SBP <math>< 100</math> mmHg and at least 30 mmHg drop in SBP (post-baseline assessments comparing to baseline);

Malignancy	Standard analyses;
Neonatal toxicity through breast milk	Standard analyses;
Renal impairment (Broad SMQ)	

1. Standard analyses;

2. For serum creatinine and eGFR, the test values and changes from baseline will be summarized by treatment group and visit, for overall and for each stratum (ACEi, ARB, No RASi), using number of observations, mean, standard deviation, median, minimum, Q1, Q3, and maximum;

3. Numbers and percentages of patients with each of the following events will be provided by treatment group, for overall and for each stratum (ACEi, ARB, No RASi);

a. eGFR decline by <math>>25\%</math>, <math>>40\%</math>, <math>>50\%</math>, and <math>>30</math> mL/min/1.73 m^2 (post-baseline assessments comparing to baseline);

b. Serum creatinine increase by <math>>50\%</math> and <math>>0.5</math> mg/dL (post-baseline assessments comparing to baseline);

c. Post-baseline serum creatinine <math>>2.0</math> mg/dL, <math>>2.5</math> mg/dL, <math>>3.0</math> mg/dL;

Safety Topic of Interest	Analysis
	4. Standard analyses within the subgroups: patients with baseline eGFR < 60 mL/min/1.73 m  and ≥ 60 mL/min/1.73 m  ;
Renal impairment (Narrow SMQ)	Standard analyses;
Rhabdomyolysis and Myoglobinuria	Standard analyses;
Statin drug drug interaction	Standard analyses;

The following subgroup analyses will be based on selected subgroup variables (Section 2.2.1).

- Treatment emergent SAEs will be summarized within each subgroup, by treatment group, SOC and PT.
- Numbers and percentages of patients with any TEAE within the safety topic name (or SOC/PT within safety topic name) for identified and potential safety topics will be provided within each subgroup, by treatment group, safety topic name, SOC, PT and maximum severity.

The SAF will be used for the subgroup analyses.

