9.5.2 Safety variables

The safety and tolerability assessments are listed below:

- Identified and potential risks (including angioedema, hyperkalemia, hypotension, renal dysfunction, liver)
- AEs and SAEs
- Sitting systolic, diastolic BP, and pulse pressure
- Heart rate
- Symptomatic hypotension
- Angioedema
- Hyperkalemia
- Renal dysfunction
- Other relevant laboratory values
- ECG changes

The assessment of safety will be based primarily on the frequencies of AEs, SAEs, and laboratory abnormalities. Other safety data will be summarized as appropriate.

The incidence of treatment-emergent AEs (new or worsened) will be summarized by primary system organ class, preferred term, severity, and relationship to study drug. In addition, the incidence of death, SAEs, and AEs leading to discontinuation will be summarized separately by primary system organ class and preferred term.

The incidence of AEs related to the identified and potential risks will be summarized by SMQ preferred terms.

Laboratory data will be summarized by presenting shift tables using extended normal ranges (baseline to most extreme post-baseline value), by presenting summary statistics of raw data and change from baseline values (mean, medians, standard deviations, ranges) and by the flagging of notable values in data listings. LFT categorical analysis will also be provided.

Data from other tests (eg ECG or vital signs) will be listed, notable values will be flagged, and any other information collected will be listed as appropriate.

Safety analyses will be performed based on the SAF. There will be no formal statistical inference analysis.

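### SAP Table 2-9, hepatotoxicity row (w), keeps *or* after reversing the transaminase inequality, so it also counts patients with one enzyme above 3 × ULN

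*SAP*

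**What the plan says.** Item 3 of the hepatotoxicity entry in SAP Table 2-9 lists 24 laboratory or laboratory-plus-symptom events, (a) to (x). For these, "Numbers and percentages of patients with each of the following events will be provided by treatment group", overall and within each RASi stratum. Three rows matter here.

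- Row (w) opens with "TBL > 3 × ULN) and [(AST ≤ 3 × ULN". Its transaminase ceiling in full is "AST ≤ 3 × ULN) or (ALT ≤ 3 × ULN", and it also requires ALP at or below 1.5 × ULN.
- Row (u) is "ALT > 3 × ULN) or (AST > 3 × ULN)] and (TBL > 2 × ULN) and (ALP ≤ 2 × ULN".
- Row (x) takes ALP above 3 × ULN "and AST, ALT, TBL are within normal range".

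SAP section 2.8.3.2 runs the same hepatotoxicity analyses separately on local and central laboratory data. Protocol section 9.5.2 says of safety: "There will be no formal statistical inference analysis". None of the rows (u), (w) and (x) has a descriptive label, and neither document explains the *or* in row (w).

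**The concern.** Wherever the other rows define transaminase elevation, they join ALT and AST with *or* and use a greater-than sign. That is right, because one raised enzyme is enough. Row (w) turns the inequality round to set a ceiling but keeps *or*. A ceiling joined by *or* is met as soon as one enzyme is low, however high the other is.

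Hepatotoxicity is named in Protocol section 3.6 as a potential risk of LCZ696. Someone who uses row (w) to see how many patients had raised bilirubin without raised transaminases would get a count that includes patients with a marked rise in one transaminase. Liver events of this kind are usually few, so even one or two such patients could change the row.

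**Working it through.** There is no planned figure to reproduce, so this is a check of logic. All values are multiples of ULN. The definitions come from SAP Table 2-9.

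**1. Complement of the elevation condition.** Elevation is (ALT > 3 or AST > 3). Its complement is (ALT ≤ 3 *and* AST ≤ 3). Row (w) instead has (AST ≤ 3 *or* ALT ≤ 3), which fails only when ALT > 3 and AST > 3 together.

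**2. Overlap with row (u).** Take any patient with exactly one enzyme > 3, TBL > 3 and ALP ≤ 1.5. The other enzyme is ≤ 3, so row (w) is met. For row (u), one enzyme is > 3, TBL > 3 implies TBL > 2, and ALP ≤ 1.5 implies ALP ≤ 2, so row (u) is met as well. The overlap therefore holds for every such patient.

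**3. Individual cases,** with TBL 3.5 and ALP 1.0:

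| ALT | AST | (w) as written | (w) with *and* | (u) |
|---|---|---|---|---|
| 1 | 1 | yes | yes | no |
| 10 | 1 | yes | no | yes |
| 1 | 10 | yes | no | yes |
| 25 | 2.9 | yes | no | yes |
| 2.9 | 25 | yes | no | yes |
| 10 | 10 | no | no | yes |

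As written, a patient with ALT 10 and AST 1 is in row (w), but a patient with both at 10 is not. The two cases at 25 also meet row (k), the transaminase > 20 row.

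**4. Grid of values.** Use nine levels for each enzyme, four of them ≤ 3 (0.5, 1, 2, 3) and five > 3 (3.1, 5, 8.1, 10.1, 20.1). This gives 9 × 9 = 81 pairs.

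- As written, row (w) admits 81 − 5 × 5 = 56 pairs. Of these, 56 − 4 × 4 = 40 also meet row (u).
- With *and*, row (w) admits 4 × 4 = 16 pairs, and none meets row (u).

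The pairs show the logic only. They are not patient frequencies.

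**5. What is still captured.** A patient with ALT 10, AST 2.5, TBL 4 and ALP 1 is counted in (a), (b), (c), (f), (g), (h), (i), (o), (p), (q), (u) and (v). The *or* adds (w) to that list and removes nothing from it.

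**6. Evidence on purpose.** Row (q) already counts TBL > 3 alone, so all that row (w) adds is its ceilings on transaminases and ALP. A ceiling that admits ALT 25 with AST 2.9 does not do that job. The adjacent row (x) demands that every other test be in range. Protocol Table 14-2 gives isolated bilirubin elevation a category of its own, apart from potential Hy's Law cases, and Protocol Table 14-1 needs only one raised transaminase for the latter.

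**The case against.** The purpose of row (w) is inferred. The SAP gives it no name, and the parallels are imperfect. Row (x) requires normal values, whereas row (w) tolerates transaminases up to 3 × ULN. The protocol's isolated bilirubin categories start at 1.5 and 2 × ULN, not 3. This stands, and it is why the intent can only be called likely.

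The rows are not exclusive classes. Rows (b) to (e) nest in (a), (g) to (k) nest in (f), (u) lies inside (g), and (v) contains (u). Appearing in several rows is normal in this table, so overlap alone is not an error. This also stands. The point is that row (w) is wider than its ceilings suggest.

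A reader might infer that potential Hy's Law cases are being relabelled as a benign pattern, or hidden. The documents do not support that. The row (u) count is unaffected. Nothing in either document calls raised bilirubin benign: Protocol Table 14-1 lists TBL above 2 × ULN as a liver event, absent known Gilbert syndrome, and Table 14-2 attaches actions to the isolated form. Nor is every patient in the overlap a confirmed potential Hy's Law case, because Table 14-1 also asks for a mainly conjugated fraction, which neither row checks.

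**Conclusion.** Row (w) is wrong as written if, as is likely, it is meant to count bilirubin elevation without transaminase elevation. It then overcounts by exactly the patients with one enzyme above 3 × ULN, TBL above 3 × ULN and ALP at or below 1.5 × ULN. The error can only raise the row, never lower it.

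The size is small: one of 24 descriptive rows, repeated by stratum and by laboratory source. It has no bearing on efficacy, on any other hepatotoxicity row, or on patient follow-up, which is governed by the protocol's liver tables.

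The conclusion rests on two assumptions: the inferred purpose of the row, and that all values for a row come from the same sample. Table 2-9 does not state the second for the liver rows, although its hypotension item 3(c) does ask for simultaneous values. Without it, a patient could meet the corrected row (w) at one visit and row (u) at another.

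**What to change.** Rewrite row (w) as: (TBL > 3 × ULN) and (AST ≤ 3 × ULN) and (ALT ≤ 3 × ULN) and (ALP ≤ 1.5 × ULN). Update the table program to match before database lock. If the *or* was deliberate, the SAP should instead state what row (w) is meant to measure.

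The cost is one connector in the SAP and the corresponding line of the program. No data collection, sample size or other analysis changes.

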6.5.4 Laboratory evaluations

A central laboratory will be used for analysis of all specimens collected. Details on the collection, shipment of samples and reporting of results by the central laboratory are provided to investigators in the laboratory manual.

Clinically notable laboratory findings are defined in [Appendix 1](#).

Complete laboratory evaluations such as hematology and blood chemistry ([Table 6-2](#)) for the assessment of safety in this study will be performed at Visits 1, 101, 105 and 199/PSD.

Abbreviated laboratory evaluations will be performed as indicated in [Table 6-1](#). Abbreviated central laboratory includes: BUN, creatinine, potassium, and eGFR.

In addition to the required central laboratory assessments, a local laboratory may be used for the assessment of creatinine, potassium and eGFR during the up-titration period as indicated in [Table 6-1](#). The results from the local laboratory during the up-titration period will be allowed to be used for decision making regarding the eligibility of the patient to continue on in the study and will be recorded on the appropriate eCRF. In addition, local laboratory assessments may be performed on an as-needed basis to monitor tolerability to study drug at unscheduled visits during the randomized treatment period and will be recorded in the appropriate eCRF.

Laboratory values that exceed the boundaries of a notable laboratory abnormality ([Appendix 1](#)) must be commented on by the investigator in the patient's eCRF and additional laboratory evaluations should be performed, as judged appropriate by the investigator. If the laboratory abnormality induces clinical signs or symptoms, or requires therapeutic intervention, then the diagnosis or medical condition must be entered on the AE eCRF. If the laboratory abnormality is the primary reason for an unforeseen hospitalization or otherwise fulfills the seriousness category of an AE, then the procedure for rapid notification of SAEs must be followed. If the laboratory abnormality leads to study drug discontinuation (temporarily or permanently), the patient must be followed until the abnormality resolves or until it is judged to be permanent. The investigation may include continued monitoring by repeat laboratory testing or by performing additional laboratory tests as deemed necessary by the investigator or the Novartis medical monitor.

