16 Appendix 4 – Treatment guidelines for hyperkalemia (serum potassium* greater than 5.3 mmol/L [mEq/L])

General principles

Elevation of potassium levels above the predefined values should be repeated and confirmed before any action is taken.

Any patient with a serum potassium* > 5.3 mmol/L (mEq/L) at any time after randomization requires the Investigator to confirm the potassium concentration in a non-hemolyzed sample via an immediate repeat lab sample to both the clinic local lab and the study central lab. Regular, repeated checks of potassium concentration (beyond that prescribed in the protocol) should continue until it is clear that the potassium concentration is stable and not rising into the range of concern (≥ 5.5 and < 6.0 mmol/L [mEq/L]) or potential danger (≥ 6.0 mmol/L [mEq/L]).

Patients with elevated potassium value will be managed according to the corrective actions outlined below. Hyperkalemia should be followed until resolution.

Corrective action for management of hyperkalemia

Serum potassium* greater than 5.3 and less than or equal to 5.5 mmol/L (mEq/L)

1. Confirm potassium concentration in a non-hemolyzed sample
2. Reinforce low potassium diet and restriction of food/drinks with high potassium content (eg orange juice, melon, bananas, tomatoes, dried fruits, potatoes, low-salt substitutes, tomatoes, coffee, etc.)
3. Correct metabolic acidosis if necessary.
4. Review medical regimen (including dietary supplements and over-the-counter medications) for agents known to cause hyperkalemia. Consider reduction in dose or discontinuation of these agents:
 - MRAs (if they are believed to be the most likely cause of hyperkalemia)
 - Potassium-sparing diuretics (eg amiloride and triamterene) including in combination products with thiazide or loop diuretics
 - Potassium supplements, eg potassium chloride
 - Salt substitutes
 - Non-steroidal anti-inflammatory drugs (NSAIDs)
 - Cyclo-oxygenase-2 (COX-2) inhibitors
 - Trimethoprim and trimethoprim-containing combination products, such as Bactrim[®] and Septra[®] (trimethoprim/sulfamethoxazole fixed combination)
 - Herbal Supplements:
 - For example, Noni juice, alfalfa (*Medicago sativa*), dandelion (*Taraxacum officinale*), horsetail (*Equisetum arvense*), nettle (*Urtica dioica*), milkweed, lily of the valley, Siberian ginseng, hawthorn berries

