5. Assess patient for dehydration or any condition that could lead to dehydration (e.g., diarrhea, vomiting) and/or hypovolemia and initiate appropriate corrective measures of rehydration.
6. Repeat serum potassium* measurement within 3 to 5 days
 - If serum potassium* remains > 5.3 and ≤ 5.5 mmol/L (mEq/L), regularly monitor serum potassium* levels to ensure stability (suggested once monthly)
 - Consider down-titration of study drugs, according to investigator's medical judgment.

Serum potassium* greater than 5.5 and less than 6.0 mmol/L (mEq/L)

- Confirm potassium concentration in a non-hemolyzed sample
- Consider down-titration or temporarily discontinue study drugs according to investigator medical judgment.
- Apply all measures outlined for serum potassium* > 5.3 and ≤ 5.5 mmol/L
- Repeat serum potassium* measurement after 2-3 days
- If serum potassium* < 5.5 mmol/L, consider resumption of study drugs at lower dose with repeat potassium within 5 days

Serum potassium* greater than or equal to 6.0 mmol/L (mEq/L)

- Immediately discontinue study drugs
- Confirm potassium concentration in a non-hemolyzed sample
- Urgently evaluate patient and treat hyperkalemia as clinically indicated
- Apply all measures outlined for serum potassium* > 5.3 and < 6.0 mmol/L (mEq/L)

No resumption of study drugs without individualized case discussion with and permission from Novartis medical monitor or his/her designee.

* or equivalent plasma potassium value

17 Appendix 5 – Guidelines for the management of hypotension

Guidelines

1. Investigator should monitor BP closely
2. If symptomatic hypotension occurs:
 - a. Correct any treatable cause, eg hypovolemia
 - b. If hypotension persists, any antihypertensive drug such as diuretics, calcium channel blockers (CCBs), nitrates, beta blockers, aldosterone antagonists and α -blockers, should be down-titrated or stopped first before down-titration of the study drugs are considered. Any non-antihypertensive drug (such as nitrates) should be considered for down-titration prior to study drug as determined by the best judgment of the investigator.
 - c. If hypotension persists, the study drugs should be down-titrated or even temporarily withdrawn. The dose re-challenge and medications adjust guidelines described in [Section 5.5.5](#) should be adhered to as much as possible.

18 Appendix 6 – Six-minute walk test

[figure not shown]

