**Table 2-10 Complete laboratory evaluations**

Hematology	Biochemistry	Urine measurements
Hematocrit	Alanine aminotransferase (ALT)	Urinalysis
Hemoglobin	Albumin (Alb)	
Platelet count	Alkaline phosphatase (ALP)	
Red blood cell count (RBC)	Aspartate aminotransferase (AST)	
White blood cell count (WBC)	Blood urea nitrogen (BUN)*	
WBC differential	Calcium	
Red blood cell distribution width (RDW)	Chloride	
Mean corpuscular volume (MCV)	Creatinine*	
Mean corpuscular hemoglobin concentration (MCHC)	eGFR*	
	Glucose	
	Hemoglobin A1C	
	Lipid profile (total cholesterol, LDL, HDL, and triglycerides)	
	Phosphate	
	Potassium*	
	Serum pregnancy test	
	Sodium	
	Total bilirubin (TBL)	
	Fractionated bilirubin (if total bilirubin > 2 x upper limit of normal range [ULN])	
	Total protein	
	Uric acid	

\*Laboratory assessments for the abbreviated laboratory evaluation at visits where the complete laboratory evaluation is not performed

Both complete laboratory evaluations and abbreviated laboratory evaluations will be included in the summaries for laboratory data. In general, local lab and central lab data will be analyzed separately.

For the laboratory assessments, if the test value is below the LLOQ, the test value will be imputed by  $0.5 \times \text{LLOQ}$ ; if the test value is above the ULOQ, the test value will be imputed by  $1.5 \times \text{ULOQ}$ .

For each laboratory parameter, the baseline assessment is defined as the last non-missing central laboratory assessment (scheduled or unscheduled) prior to or on the first dose date of the study drug.

Test values and change from baseline in test values based on the central laboratory assessment will be summarized, separately, for overall and for each stratum (ACEi, ARB, No RASi), by laboratory parameter, treatment group and visit, using number of observations, mean, standard deviation, median, minimum, Q1, Q3, and maximum.

For each laboratory parameter and each specific assessment, the test value will be categorized into normal, low, or high, according to the corresponding normal range.

For each laboratory parameter and each specific post-baseline visit, the shift from baseline to the visit is defined as the shift from the baseline category to the categorized post-baseline test value (low to low, low to normal, low to high, normal to low, normal to normal, normal to high, high to low, high to normal, high to high).

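### The planned hyperkalemia table counts potassium >6.0 mEq/L, while the protocol's immediate-stop level is ≥6.0, so no planned table gives the per-arm count at or above that level

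*SAP*

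**What the plan says.** **SAP Table 2-9, Hyperkalemia.** Item 4 gives "Numbers and percentages of patients with any post-baseline serum potassium" ≥5.5, >6.0 and >6.5 mEq/L, by treatment group, overall and within each RASi stratum. The first cut is inclusive and the other two are strict. Items 2 and 3 count treatment-emergent hyperkalemia that led to interruption or permanent discontinuation of study treatment.

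**Protocol Appendix 4, general principles.** Potassium is to be followed until it is clearly not rising into the "range of concern (≥ 5.5 and < 6.0 mmol/L [mEq/L]) or potential danger (≥ 6.0 mmol/L [mEq/L" range.

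**Protocol Appendix 4, corrective actions.** The action bands are >5.3 to ≤5.5, >5.5 to <6.0, and the top band, headed "Serum potassium* greater than or equal to 6.0 mmol/L (mEq/L". The first instruction in the top band is "Immediately discontinue study drugs". The general principles also say that raised values "should be repeated and confirmed before any action is taken".

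**SAP Section 4** records no change from the protocol-specified analyses. The SAP gives no reason for the strict sign at 6.0.

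**The concern.** Hyperkalemia is one of the risks that Protocol 3.6 lists as common to LCZ696, enalapril and valsartan, and it is a named safety topic in the SAP. A reader of the safety tables will naturally ask how many patients in each arm reached the level at which the protocol tells the investigator to stop treatment. The planned rows do not quite answer that. One is too wide (≥5.5), and the next leaves out the boundary value itself (>6.0). If potassium is reported to one decimal, exactly 6.0 may be among the more common values at or above the stop level, because the distribution falls away quickly in that tail.

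**Working it through.** **1. The two thresholds.** The protocol's set is {maximum ≥6.0} and the SAP's set is {maximum >6.0}. They differ only by patients whose maximum is exactly 6.0. Write R1 for the ≥5.5 row, R2 for the >6.0 row, and x for the number with a maximum of exactly 6.0. Then

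count at ≥6.0 = R2 + x, with 0 ≤ x ≤ R1 − R2.

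The planned rows give R1 and R2 but not x, so they only bracket the count at ≥6.0 between R2 and R1.

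**2. Whether another planned table supplies x.**

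| Planned output | Where | Why it does not give the count at ≥6.0 |
|---|---|---|
| Shift tables, minimum/maximum category | SAP 2.8.3.1, Table 2-11 | Classes are low, normal and high only |
| By-visit statistics | SAP 2.8.3.1 | Report a maximum, not a count above a level |
| Clinically notable values | SAP Table 2-12, Protocol Appendix 1 | Change of >20% from baseline, at any end level |
| Hyperkalemia items 1 to 3 | SAP Table 2-9 | Count adverse events, not potassium levels |
| Flagged listings | Protocol 9.5.2 | Patient-level, not a count per arm |

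None of them does.

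**3. Possible size (illustration only).** The documents give no potassium distribution and no reporting precision. The only document-based inputs are about 1,250 patients per arm (2,500 randomized 1:1) and seven scheduled post-baseline samples (Weeks 2, 4, 8, 12, 16, 20 and 24). With h equal to half the reporting unit,

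x = 1,250 × [P(max ≥ 6.0 − h) − P(max ≥ 6.0 + h)].

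*Model A.* Seven equally correlated normal values; assumed mean 4.5 and correlation 0.5. Patients per arm:

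| SD | Reporting unit | ≥6.0 | >6.0 | Exactly 6.0 | Share of ≥6.0 |
|---|---|---|---|---|---|
| 0.45 | 0.1 | 5.0 | 2.3 | 2.7 | 54% |
| 0.50 | 0.1 | 13.8 | 7.4 | 6.4 | 46% |
| 0.45 | 0.01 | 3.5 | 3.3 | 0.26 | 7% |
| 0.50 | 0.01 | 10.5 | 9.9 | 0.63 | 6% |

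With heavier tails (t with 3, 4, 5 and 10 degrees of freedom, scaled to the same SDs, simulated), 0.1 reporting gives 4.3 to 8.7 patients at exactly 6.0 (18% to 38%), and 0.01 reporting gives 0.45 to 0.83 (2% to 5%).

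*Model B.* The per-patient maximum taken as normal, with assumed mean 4.7 to 5.0 and SD 0.4 to 0.6, and 0.1 reporting only. Exactly 6.0 accounts for 0.6 to 20.8 patients per arm, or 29% to 58% of those at ≥6.0. At mean 4.9 and SD 0.5, for example, 22.3 − 13.4 = 8.9 patients (40%).

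Unscheduled repeat samples are not modelled. Reporting precision moves the answer most.

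**The case against.** The best case for leaving the table alone has five parts.

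- **No rule is broken.** Appendix 4 guides patient care, Protocol 9.5.2 sets no potassium cut-offs and plans no formal inference on safety, and neither document says that item 4 must follow Appendix 4. This stands. A reader might infer from SAP Section 4 that the strict sign departs from a protocol-specified analysis; it does not, because the protocol specifies no such table.
- **The SAP is strict elsewhere too.** Protocol 7.4 uses eGFR falls of ≥25% and ≥40%, and SAP Table 2-9 reports >25% and >40%. That is a fair point about house style. But an exact tie is unlikely for a percentage change in eGFR, whereas it can be common for potassium if results are rounded to 0.1.
- **Appendix 4 is not uniform.** A reader might infer that the SAP's 5.5 cut matches the protocol and only the 6.0 cut departs from it. The documents do not support that contrast. The general principles use ≥5.5, but the action bands put exactly 5.5 in the lower band. At 6.0, by contrast, both parts of Appendix 4 agree on ≥6.0.
- **Much is captured anyway.** Everyone above 6.0 is counted, and everyone at 6.0 lies inside the ≥5.5 row. If a laboratory abnormality "requires therapeutic intervention, then the diagnosis or medical condition must be entered on the AE eCRF" (Protocol 6.5.4), so many acted-on cases should reach items 2 and 3. A value of 6.0 from a baseline below 5.0 is also a rise of more than 20%. All true, but none of these counts patients by potassium level.
- **A ≥6.0 row would include unconfirmed samples.** It would, and so do the existing rows. A footnote deals with this.

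A reader might also infer that the laboratory source for item 4 is undefined, because Appendix 4 asks for confirmation "via an immediate repeat lab sample to both the clinic local lab and the study central lab", and SAP 2.8.3.2 states the source for liver and renal data only. The general rule in SAP 2.8.3.1 already covers potassium: "In general, local lab and central lab data will be analyzed separately". No change is needed there.

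**Conclusion.** The point holds as a minor, cost-free improvement. The reporting cut and the protocol's stop level differ by the single value 6.0, and the count at ≥6.0 per arm cannot be recovered from any planned table. That rests on the text alone and needs no assumption.

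The number of patients involved is unknown. The illustrations run from a fraction of a patient per arm (0.01 reporting) to about 21 (0.1 reporting with the widest assumed spread). Every distributional input behind them is assumed, so they show that the boundary could matter, not that it does. The protocol writes its potassium thresholds to one decimal, but that does not establish the laboratory's reporting precision.

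The consequence stops at one row of one descriptive safety table. It would be too strong to say that severe hyperkalemia goes unreported, since values above 6.0 are counted and the same rule applies to both arms. Efficacy results, error control and the management of patients are not affected.

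**What to change.** In SAP Table 2-9, Hyperkalemia item 4, add a ≥6.0 mEq/L row by treatment group, overall and for each stratum. Keep the >6.0 row for comparability. Add a footnote that the new row counts patients with any post-baseline value at that level, and does not count confirmed values or study drug stops, because Appendix 4 asks for a repeat before action.

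Cost: one row and one footnote in the table shell. No new data, no protocol change, and no effect on any other analysis.
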